3.5 Outcome Measures

3.5.1 Primary Outcome Measure

The primary outcome measure is the ALSFRS-R score obtained monthly for all treated participants (in person at screening/baseline, month 1, month 3 and month 6; via telephone at months 2, 4 and 5). We will also obtain this measure by phone at months 6 and 12 of the extension. For all enrolled PALS in Groups 1 and 2, we will compare the slope of ALSFRS-R progression before enrollment to the slope of ALSFRS-R progression during the trial (see Section 3.6 below). ALSFRS-R is a quickly administered (five minute) ordinal rating scale (ratings 0-4) used to determine patients' assessments of their capability and independence in 13 functional activities. All 13 activities are relevant in ALS. Initial validity was established in ALS patients by documenting their change in ALSFRS-R scores, which correlated with change in strength over time, was closely associated with quality of life measures, and predicted survival (2,11,12). The test-retest reliability is greater than 0.88 for all 13 activities. The ALSFRS-R declines linearly with time over a wide range during the course of ALS. The minimum clinically significant change in this scale is said to be 20% (2,11-13). The measure can be reliably conducted over the phone (13).

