3 DESIGN & PROCEDURES

3.1 Design Overview

This is an open label, prospective cohort study of 10 PALS from the Duke ALS Clinic (5). The first 5 enrolled PALS (Group 1) will receive standard ALS care for the first month, then standard care plus Triheptanoin for the next 5 months. The next 5 enrolled PALS (Group 2) will receive standard ALS care plus Triheptanoin for 6 months (Figure 1). All Group 1 and Group 2 PALS who complete this 6-month study will have an option for Triheptanoin treatment extension for an

additional 12 months. In addition to the PALS, there will also be 5 healthy controls enrolled (Group 3), people that do not have ALS or any other neurodegenerative disease). These participants will not receive any treatment; the only outcome measure they will complete is serum and urine biomarker testing at screening/baseline, month 1 and month 6 (Figure 1).

[figure not shown]

Figure 1: Study Treatment Schema

Human trials with Triheptanoin have demonstrated an excellent safety profile, with only rare associated gastrointestinal side effects (see the provided copy of Ultragenyx’s Investigator’s Brochure (IB) and references 6-9). However, it has never been studied in PALS. To mitigate the risks of rare gastrointestinal side effects, all our participants will be followed by a nutritionist for the duration of this study.

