3.6 Statistical Analysis

The primary analysis is the slope of the revised ALSFRS-R during treatment compared to pre-treatment. Pre-treatment slope for each participant will be estimated as follows: (48-enrollment ALSFRS-R)/months since symptom onset. This frequently used “pre-slope” method is simple and inexpensive, and can predict disease progression as well as more complicated and expensive tools, at least for periods of less than 1 year (20).

Table 3 shows the results for the power analysis assuming that 10 patients are included in the clinical trial. The power of a test is defined as probability of the statistical test to reject a false null hypothesis, thus it quantifies the ability of a test to detect an effect, if the effect actually exists. In Table 3, the power is expressed as a percentage and the standard deviation is given in parenthesis. The number of observations were assumed to occur one per month after the beginning of the trial. The percentage of change in the slope of ALSFRS-R as function of time is measured against the pre-trial rate of decline. For each combination of slope percentage change and number of observations, 1000 samples were randomly generated assuming the following parameters:

- The ALSFRS-R score at the beginning of the treatment was uniformly distributed in the range [2, 40].
- The pre-trial slope was log-normally distributed with mean 0.90 (per month), and standard deviation 0.27. Thus, the range of pre-trial slopes is approximately [0.25, 3.38].
- The measurement error for the ALSFRS-R was assumed to be normally distributed with zero mean and standard deviation 0.7. This way the inter-quartile range is approximately [-0.5, 0.5].

Table 3: Power Analysis Based on 10 Patients. Power percentage along with standard deviation in parenthesis for detecting a change in the slope of ALSFRS-R with respect to time using 10 patients in a clinical trial setting. The power is given as function of both the number of observations and the percentage of change in the slope.

Number of observations (per patient)	Slope percentage change (compared to pre-trial rate of decline)				
	10%	20%	30%	40%	50%
4	5.8 (0.7)	21.6 (1.3)	49.4 (1.6)	78.8 (1.3)	94.8 (0.5)
5	9.7 (0.9)	44.6 (1.6)	81.8 (1.2)	97.2 (0.5)	99.6 (0.7)
6	19.4 (1.3)	69.9 (1.5)	97.5 (0.5)	99.9 (0.1)	100.0 (0.0)
7	30.3 (1.5)	88.2 (1.0)	99.7 (0.2)	100.0 (0.0)	100.0 (0.0)

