The results indicate that a 20% change in the slope, compared to pre-trial rate of decline, can be detected with power 88.2% (1.0%) with 7 observations (six months trial - baseline observation plus one observation monthly).

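### The primary ALSFRS-R slope is defined in two ways that differ for Group 1, and the 88.2% power describes neither version of the delayed-start design

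*Combined protocol and SAP*

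**What the plan says.** Section 3.5.1 sets the primary comparison for all patients in Groups 1 and 2: "we will compare the slope of ALSFRS-R progression before enrollment to the slope of ALSFRS-R progression during the trial". It refers the reader to Section 3.6, which opens: "The primary analysis is the slope of the revised ALSFRS-R during treatment compared to pre-treatment". Section 3.6 then fixes the reference slope at enrollment: "Pre-treatment slope for each participant will be estimated as follows: (48-enrollment ALSFRS-R)/months since symptom onset".

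Section 3.1 states that Group 1 "will receive standard ALS care for the first month, then standard care plus Triheptanoin for the next 5 months". Table 1 agrees, since at baseline drug is dispensed to Group 2 only. Section 3.3 gives the month-1 MR spectroscopy comparison as the reason for the delay and does not mention the primary slope.

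The power text in Section 3.6 sets each starting score at the start of treatment (uniform, 2 to 40) but counts visits from the start of the trial: "The number of observations were assumed to occur one per month after the beginning of the trial". The stated power for a 20% change, 88.2%, is that of 10 patients "with 7 observations (six months trial - baseline observation plus one observation monthly". Neither the two groups nor a lag is mentioned.

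**The concern.** For Group 2, trial and treatment start together, so the two definitions agree. For Group 1, half of the treated patients, the month 0–1 interval lies inside the trial but outside treatment. Under 3.5.1 it is counted as exposure. Under 3.6 it belongs to neither slope, because the pre-slope formula stops at enrollment. The plan does not say where that interval goes.

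The definitions also differ on scores taken after a patient stops drug. Section 5.2 encourages such patients to stay in the protocol, so those scores will exist.

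Two things are at stake. In an open-label trial, the primary slope for half the patients could be chosen after the data are seen. And the 88.2% supporting the sample size is not the power of the analysis under either definition.

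**Working it through.** **Inputs.** From Section 3.6: 10 patients; monthly scores at months 0 to 6; measurement-error SD 0.7; "The pre-trial slope was log-normally distributed with mean 0.90 (per month), and standard deviation 0.27"; starting score uniform on 2 to 40; 20% slowing. From Sections 3.1 and 3.3: five patients start drug at month 1 and five at month 0. Assumed, because the plan does not say: a least-squares slope per patient, a t-test on the 10 differences (pre-slope minus trial slope), full effect from first dose, and no floor at a score of 0.

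**Step 1: the plan's own figure.** Without a stated test or alpha, 88.2% cannot be strictly reproduced. I compared candidate settings with all 20 cells of Table 3, with no delayed start.

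- A: pre-slope known, mean 0.90 and SD 0.27 on the natural scale, two-sided 2.5%. RMS error is 2.0 points, and the 20%/7-observation cell gives 88.2%.
- B: pre-slope known, median 0.90 and log-scale SD 0.27, one-sided 1%. RMS error is 1.3 points, and the same cell gives 88.4%.
- C: pre-slope estimated by the plan's formula, natural scale, two-sided 5%. RMS error is 5.5 points. The cell gives 88.8%, but the 4-observation, 20% cell gives 32.3% against the stated 21.6%.

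Table 3 is therefore well matched by a simulation in which all 10 patients are treated from month 0 and the pre-slope is known.

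**Step 2: dilution under 3.5.1.** For t = 0,…,6 the mean is 3 and the sum of squares is 28. The untreated month enters the fitted slope with weight Σ(t−3)·min(t,1)/28 = (−2−1+0+1+2+3)/28 = 3/28 = 0.107.

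- Group 1 shows 20% × 25/28 = 17.9%.
- All ten show 20% × (1 + 25/28)/2 = 18.9%, which is 1.1 points below the hypothesised effect.

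**Step 3: precision under 3.6.** Group 1's months 1 to 6 have sum of squares 17.5.

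- Seven scores: SE = 0.7/√28 = 0.132 points per month.
- Six scores: SE = 0.7/√17.5 = 0.167 points per month.

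Table 3 itself brackets the result: 69.9% with six observations in everyone and 88.2% with seven. Five patients with each lies between.

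**Step 4: power with the delay (20% slowing, 200,000 simulated trials per cell).** The estimated pre-slope is (48 − observed enrollment score)/months since onset, with months since onset = (48 − true score)/true slope.

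| Setting | All 10 from month 0 | 5 + 5, during treatment | 5 + 5, during the trial |
|---|---|---|---|
| A, pre-slope known | 88.2% | 79.1% | 84.5% |
| B, pre-slope known | 88.4% | 79.3% | 84.7% |
| A, pre-slope estimated | 79.1% | 74.0% | 74.5% |
| B, pre-slope estimated | 78.6% | 73.4% | 73.9% |
| C, pre-slope estimated | 88.8% | 84.9% | 85.4% |

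**Step 5: splitting the fall.** Estimating the pre-slope alone costs 88.2 − 79.1 = 9.1 points in A and 88.4 − 78.6 = 9.8 in B. The delay then costs 79.1 − 74.0 = 5.1 or 79.1 − 74.5 = 4.6 in A, and 78.6 − 73.4 = 5.2 or 78.6 − 73.9 = 4.7 in B.

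**The case against.** *Section 3.6 governs.* Section 3.5.1 points to 3.6, which names the primary analysis, so 3.5.1 may be only shorthand. That is a fair reading, and under it the dilution disappears. But the power text in 3.6 does not follow its own opening sentence for Group 1, who then have six on-treatment scores. Section 3.6 also does not say where Group 1's first month goes.

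*The dilution is small and idealised.* This stands. Section 3.3 has a two-week taper. If the effect began only half a month after first dose, a design with no delay would itself show 20% × (1 − 1.5/28) = 18.9%. The on-treatment slope in Group 1 would show 20% × (1 − 1.25/17.5) = 18.6%, or 18.8% over both groups. Flooring true scores at 0 moves the apparent slowing by more than the delay does, to about 21.6% with no delay. The dilution figures are therefore exact only under the stated assumptions.

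*The size of the power loss rests on an alpha the plan does not give.* This also stands. With the pre-slope known at two-sided 5%, the delayed design gives 88.6% during treatment and 92.3% during the trial, both above the stated figure. But that setting gives 94.5% without a delay and fits Table 3 badly (RMS 9.2), so it does not explain the 88.2%.

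*Most of the fall to 73–74% is a different issue.* This is correct: 9–10 points come from estimating the pre-slope and about 5 from the delay. With the pre-slope estimated, the two definitions differ by only 0.5 points.

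*The simulation may have included the lag.* Its absence is inferred from the description, but the match in Step 1 supports the inference.

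*This is a pilot.* That limits the consequence. In the known-pre-slope settings checked, type I error stays nominal under either definition.

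**Conclusion.** The concern holds. The wording conflict is plain from the text and needs no simulation. For half the treated patients the primary slope depends on the section followed, and under either definition the 5 + 5 design is not the pattern described for 88.2%.

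Confidence in the dilution arithmetic is high, given a least-squares slope and full effect from first dose. Confidence in the power figures is moderate, because the test and alpha are back-fitted. The direction is firm: in every setting tried, adding the delay lowered power. The delay alone does not overturn a pilot design, but the point should be fixed because it concerns the primary analysis and a stated figure.

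**What to change.** Use one definition in Sections 3.5.1 and 3.6. Following 3.6, for example: *The treated slope is estimated from first dose (baseline in Group 2, month 1 in Group 1) to month 6 and compared with the pre-treatment slope, (48 − enrollment ALSFRS-R)/months since symptom onset.* This removes the dilution caused by Group 1's untreated month. Relative to the whole-trial slope it costs about 5 points of power if the pre-slope is treated as known, and about none if it is estimated. If the whole-trial slope is preferred, say so in both sections and state that it includes Group 1's untreated month.

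Also:

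- State whether scores after stopping drug count.
- State the test, alpha and sidedness.
- Rerun the simulation for the 5 + 5 design with the plan's own pre-slope estimator, and replace 88.2% with the result.

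The cost is one clarified definition, one rerun and a less favourable number. Stated power would fall by roughly 4 to 15 points. It falls 14–15 points, to about 73–74%, if the original simulation treated the pre-slope as known at the alphas that track Table 3. It falls about 4 points (88.8% to 84.9%) if the original already estimated it at two-sided 5%, a setting that tracks Table 3 poorly. Visits, patients and procedures do not change.

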3.5.2 Secondary Outcome Measures

Secondary outcome measures include:

MR Spectroscopy NAA/Cr ratio in motor cortex will be measured at screening/baseline and 1 month time points. This measure declines over time in patients with ALS (14-17). This measure can respond to treatment; it was shown to improve over 3 weeks in patients with ALS on riluzole compared to a group that was not on this treatment (18). We will compare the MR spectroscopy changes over 1 month in Group 1 to the MR spectroscopy changes over 1 month in Group 2.

A Serum and Urine Biomarker Panel will be obtained at screening/baseline, 1 month and 6-month time points and analyzed using liquid chromatography/tandem mass spectrometry. Laboratory, pathologic, and epidemiologic evidence clearly supports the hypothesis that oxidative stress is central in the ALS pathogenic process, particularly in genetically susceptible individuals (19). Oxidative stress biomarkers in cerebrospinal fluid, plasma, and urine are elevated, suggesting that abnormal oxidative stress is generated outside of the central nervous system. Magnitude of lipid peroxidation, measured as non-enzymatic oxidation products of arachidonic acid, F2-isoprostanes, appears the most obvious oxidative stress marker. We will measure urine F2-isoprostane metabolites (class III: iPF2 α -III, and 2,3-dinor iPF-2 α -III, class VI: iPF-2 α -VI, and 8,12-iso-iPF-2 α -VI), urine creatinine, and serum and urine glutamate, α -keto-glutarate, NADH, coenzyme A levels in all treated participants and healthy controls at screening/baseline, month 1 and month 6 time points. We will compare the biomarker changes at different time points between Groups 1, 2 and 3.

For safety monitoring: concomitant medications, vital signs, weight, physical exam and safety labs (CBC, CMP, Lipid Profile, GGT, LFT and pregnancy testing for sexually active females with child bearing potential) will be measured at screening/baseline, 1 month, 3 month, and 6-month time points. Adverse events will be monitored continuously throughout the study, as described in Section 5.1.

3.6 Statistical Analysis

The primary analysis is the slope of the revised ALSFRS-R during treatment compared to pre-treatment. Pre-treatment slope for each participant will be estimated as follows: (48-enrollment ALSFRS-R)/months since symptom onset. This frequently used “pre-slope” method is simple and inexpensive, and can predict disease progression as well as more complicated and expensive tools, at least for periods of less than 1 year (20).

Table 3 shows the results for the power analysis assuming that 10 patients are included in the clinical trial. The power of a test is defined as probability of the statistical test to reject a false null hypothesis, thus it quantifies the ability of a test to detect an effect, if the effect actually exists. In Table 3, the power is expressed as a percentage and the standard deviation is given in parenthesis. The number of observations were assumed to occur one per month after the beginning of the trial. The percentage of change in the slope of ALSFRS-R as function of time is measured against the pre-trial rate of decline. For each combination of slope percentage change and number of observations, 1000 samples were randomly generated assuming the following parameters:

- The ALSFRS-R score at the beginning of the treatment was uniformly distributed in the range [2, 40].
- The pre-trial slope was log-normally distributed with mean 0.90 (per month), and standard deviation 0.27. Thus, the range of pre-trial slopes is approximately [0.25, 3.38].
- The measurement error for the ALSFRS-R was assumed to be normally distributed with zero mean and standard deviation 0.7. This way the inter-quartile range is approximately [-0.5, 0.5].

Table 3: Power Analysis Based on 10 Patients. Power percentage along with standard deviation in parenthesis for detecting a change in the slope of ALSFRS-R with respect to time using 10 patients in a clinical trial setting. The power is given as function of both the number of observations and the percentage of change in the slope.

Number of observations (per patient)	Slope percentage change (compared to pre-trial rate of decline)				
	10%	20%	30%	40%	50%
4	5.8 (0.7)	21.6 (1.3)	49.4 (1.6)	78.8 (1.3)	94.8 (0.5)
5	9.7 (0.9)	44.6 (1.6)	81.8 (1.2)	97.2 (0.5)	99.6 (0.7)
6	19.4 (1.3)	69.9 (1.5)	97.5 (0.5)	99.9 (0.1)	100.0 (0.0)
7	30.3 (1.5)	88.2 (1.0)	99.7 (0.2)	100.0 (0.0)	100.0 (0.0)

The results indicate that a 20% change in the slope, compared to pre-trial rate of decline, can be detected with power 88.2% (1.0%) with 7 observations (six months trial - baseline observation plus one observation monthly).

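### The 88.2% power assumes every untreated patient would keep exactly their pre-trial slope, and section 3.6 does not say so

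*Combined protocol and SAP*

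**What the plan says.** Section 3.5.1 sets the primary comparison for Groups 1 and 2: "we will compare the slope of ALSFRS-R progression before enrollment to the slope of ALSFRS-R progression during the trial". Section 3.6 defines the comparator: "Pre-treatment slope for each participant will be estimated as follows: (48-enrollment ALSFRS-R)/months since symptom onset".

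The power simulation, also in section 3.6, lists three random inputs:

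- a starting score uniform on [2, 40];
- the slope: "The pre-trial slope was log-normally distributed with mean 0.90 (per month), and standard deviation 0.27";
- the score error: "The measurement error for the ALSFRS-R was assumed to be normally distributed with zero mean and standard deviation 0.7".

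The treatment effect is a fixed percentage: "The percentage of change in the slope of ALSFRS-R as function of time is measured against the pre-trial rate of decline". The conclusion drawn is that "a 20% change in the slope, compared to pre-trial rate of decline, can be detected with power 88.2% (1.0%) with 7 observations".

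Two statements support the pre-slope as comparator. Section 3.6 cites a study for the claim that it forecasts progression no worse than costlier methods over horizons under a year. Section 3.5.1 adds: "The ALSFRS-R declines linearly with time over a wide range during the course of ALS".

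**The concern.** The quantity tested is the pre-slope minus the in-trial slope. It contains any treatment effect, the score error, and the amount by which the patient would have departed from the pre-slope without treatment. The third part is absent from the simulation as described.

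Neither supporting statement fills the gap. Predicting as well as other tools is a relative claim and does not mean zero prediction error. Linear decline over a wide range is qualitative. Neither gives an error size, and neither is offered as a condition on the power. The 0.27 SD is not a substitute, because it describes spread between patients and nearly cancels within a patient.

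At stake is the only power the plan gives for its primary 20% hypothesis (section 1.2) with the planned seven scores. If it is too high, a null result could be over-read as evidence against 20% slowing.

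**Working it through.** **Inputs from section 3.6.** 10 patients; scores at months 0 to 6; score error SD 0.7; mean pre-slope 0.90 and SD 0.27 points/month; 20% slowing, so a mean effect of 0.2 × 0.90 = 0.18 points/month.

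**Assumed, because the plan does not state them.** A paired t-test (9 df) on pre-slope minus the least-squares in-trial slope; two-sided alpha 0.05 or 0.025; the 0.27 read in points/month unless noted; a zero-mean random departure with SD τ.

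**Step 1: variance of one patient's slope difference, with an error-free pre-slope.**

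- Score error: the squared deviations of months 0 to 6 sum to 28, so 0.7²/28 = 0.49/28 = 0.0175.
- Between-patient spread: (0.2 × 0.27)² = 0.0029.
- Departure: 0.64τ² if the 20% reduction also acts on the departure, that is, in-trial slope = 0.8 × (pre-slope + departure). It is τ² if the departure is added after the reduction.

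**Step 2: power from the noncentral t**, with noncentrality 0.18 / (SD/√10), for the 0.64τ² form.

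| τ | Variance | SD | Power, alpha 0.05 | Power, alpha 0.025 |
|---|---|---|---|---|
| 0 | 0.0204 | 0.143 | 94.2% | 87.7% |
| 0.05 | 0.0220 | 0.148 | 92.6% | 85.0% |
| 0.10 | 0.0268 | 0.164 | 87.0% | 76.9% |
| 0.20 | 0.0460 | 0.215 | 65.7% | 51.7% |

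Simulation agrees to within about half a point.

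**Step 3: the plan's own figure.** With τ = 0, two settings come close to 88.2%:

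- alpha 0.025 with an error-free pre-slope, about 88%;
- alpha 0.05 with the pre-slope computed from the error-containing enrolment score, about 88.5%.

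Enrolment error costs power because a score that reads high at month 0 both lowers the pre-slope and steepens the fitted in-trial decline.

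The first setting also tracks the 20% column of Table 3: 24.1, 46.6, 69.9 and 87.8%, against the stated 21.6, 44.6, 69.9 and 88.2%. Over the whole table its mean absolute error is 1.4 points (maximum 4.2). Adding a departure (τ² form) raises that mean error to 1.6 at τ = 0.05, 4.6 at 0.10 and 15.2 at 0.20. No setting matched every cell within 2 points, and these settings were picked after the fact, so the match only corroborates the listed inputs.

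**Step 4: power by setting** (points/month reading).

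| Setting | Departure term | τ = 0 | τ = 0.10 | τ = 0.20 |
|---|---|---|---|---|
| alpha 0.025, error-free pre-slope | reduced by 20% | 88% | 77% | 52% |
| alpha 0.025, error-free pre-slope | not reduced | 88% | 71% | 40% |
| alpha 0.05, enrolment error included | reduced by 20% | 89% | 81% | 61% |
| alpha 0.05, enrolment error included | not reduced | 89% | 77% | 51% |
| alpha 0.05, error-free pre-slope | reduced by 20% | 94% | 87% | 66% |
| alpha 0.05, error-free pre-slope | not reduced | 94% | 83% | 54% |

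**Step 5: other readings of the 0.27** (error-free pre-slope, departure reduced; τ = 0, 0.10, 0.20).

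- Natural-log scale: about 96, 90 and 69% at alpha 0.05; 91, 81 and 55% at alpha 0.025.
- Log10 scale: about 92, 86 and 69% at alpha 0.05; 82, 74 and 54% at alpha 0.025.

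For scale, τ = 0.10 is 0.10/0.90 = 11% of the mean slope and τ = 0.20 is 22%. A zero-mean departure leaves the type I error near its nominal level, so the cost is in power.

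**The case against.** The strongest reply is that the model is disclosed. Section 3.6 lists its parameters, and the text, the Table 3 header and the conclusion all name the pre-trial rate as reference. Every power figure is conditional on its inputs, so what is missing is a sensitivity analysis. This stands in part, since the comparator is named. Naming it does not tell the reader that untreated patients are assumed to keep that rate exactly.

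Second, the departure SD is invented, and the loss runs from negligible to large depending on it. That stands. It rules out a single corrected figure, but it equally means the plan has no basis for an unqualified 88.2%.

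Third, the stated slope range of about [0.25, 3.38] lies at −2.06 and +2.13 SD around 0.90 on the log10 reading, and beyond 4 SD on the other two. If it is a central interval of about 95%, log10 fits best, and the loss at τ = 0.10 is then somewhat smaller (92% to 86% at alpha 0.05). The range could instead be simulated extremes. Power still falls on every reading.

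Fourth, what the simulation contained is inferred from a list. A small unlisted departure cannot be excluded: in the best-fitting setting, τ = 0.05 fits Table 3 almost as well as zero.

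Finally, this is a 10-patient open-label pilot concerned with safety and promising signals, and Table 3 also covers larger effects. That limits the consequences. But the plan itself sets a primary efficacy hypothesis of at least 20% slowing and quotes its power to one decimal.

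**Conclusion.** The concern holds and should be fixed. As described, the 88.2% is conditional on no random departure of the untreated in-trial slope from the pre-slope, and the plan does not say so.

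In the two settings closest to the stated figure, an assumed departure SD of 0.10 points/month brings power to about 71–81%, and 0.20 to about 40–61%. At alpha 0.05 with an error-free pre-slope and the departure also reduced by 20%, an SD of 0.05–0.10 still leaves about 87–95% on the points/month and natural-log readings.

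These figures illustrate sensitivity and are not the trial's actual power. They rest on an assumed test, alpha and departure SD, and they keep the plan's simplification of seven treated scores in all 10 patients, although Group 1 is untreated in its first month. A systematic gap between untreated decline and the pre-slope would be a bias; it is a separate matter and is not counted here.

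**What to change.** - State the test, the alpha and its sidedness, and the scale on which the 0.27 SD applies; the rerun needs all of these.
- Rerun the simulation with the pre-slope computed by the section 3.6 formula from the error-containing enrolment score. Set each patient's untreated in-trial slope to the pre-slope plus a random departure, over a stated range of SDs, and say whether the 20% reduction applies before or after the departure.
- Replace the unqualified 88.2% with the resulting range, described as conditional on the departure SD.
- As a useful addition, report the mean slope change with a confidence interval.

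The cost is a few lines of simulation code and revised text. Sample size, visits and test stay as they are. The drawback is a less favourable stated power.
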